#### **24. LOCAL RECRUITMENT METHODS**

Subjects will be recruited from the Wilderness Medical Society 2018 Everest Experience Trek to Basecamp participants. This is an annual CME trip organized by the Wilderness Medical Society in which participants ascend from Kathmandu to Everest Base Camp and return. The CME trip

**H00014860 Acetazolamide on High-Altitude Pulmonary Edema**

**Version 2 – 02/10/2018**

**INVESTIGATOR STUDY PLAN**

usually has between 20-30 participants. We will aim to recruit all eligible subjects from this group.

We will contact trip participants by email with study after they register for the trip. This recruitment email has been included in this submission.

As the WMS Trip gives required CME presentations in English, all trip participants speak English. We will not enroll adults unable to consent, minors under age 18, pregnant women, prisoners, or non-English speaking subjects.

Subjects will not be compensated or paid to participate in the study.

**25. LOCAL NUMBER OF SUBJECTS**

See #24. All subjects will be recruited from the Wilderness Medical Society 2018 Everest Experience Trek to Basecamp participants with a goal of 20-30 participants depending on the size of the CME trip registrants (exact number not available until registration closes in early 2018.)

**26. CONFIDENTIALITY**

Data will be collected including patient's vital signs and will be recorded with ultrasound images and data collection sheet. This information will be obtained from the study subject via pulse oximetry. The medical record will not be accessed. Digital images of ultrasound exams will be recorded for later review as described. Ultrasound images are recorded and stored on the password-protected encrypted handheld Android tablets during the duration of the trek. These images will be transferred to a secure password-protected hard drive in the locked offices of the Division of Emergency Ultrasound once back in the United States. Access to these images will be limited to study personnel and the UMASS IRB.

No patient identifiers (e.g. name, medical record number) will be linked to this information. A unique subject ID will be used to track data and link to ultrasound images. Final results of image interpretation by expert reviewer will be stored in an Excel spreadsheet in the UMass servers.

Only study personnel and the UMASS IRB will have access to the data. All study paperwork including electronic database information will be maintained for 3 years following completion of the study.

In the case that subjects are suspected of having HAPE during the trek, subject's information may be shared with trek leaders. Subject information may be subjected to different or fewer confidentiality protections than exist under US regulations, because the research is being conducted internationally. It is possible, although unlikely, that information may be shared with trek leaders, other medical personnel, or otherwise subject to subpoena in cases of severe illness/injury or death.

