### 11. PROCEDURES INVOLVED\*

After informed consent has been obtained, subjects will be randomized to receive either of the study medications medication: 250mg of acetazolamide or a placebo pill. Investigator will be blinded as to which arm of the study the patient is enrolled. Medications will be obtained from the UMass Pharmacy in individual blister packs. We will ensure that acetazolamide and the chosen placebo pill look similar. Any identifying information on the blister pack will be obscured by a black marking pen, if necessary. Medications will then be inserted into small opaque envelopes and marked with only a number. Numbers will be assigned to medications by use of the random number generator function (=RANDBETWEEN(1,30\*)) (\*The final number will depend on the total number of subjects) in Excel with the top half of the list being assigned Acetazolamide and the bottom half placebo pill. The list will then be sorted in numerical order in Excel. When a subject enrolls, a number will be assigned in order. Blinding of the numbers and assigned medications as well as the assembly of the envelopes will be done prior to leaving UMass by PI's faculty advisor who will not be involved in medication administration.

At each of the time points noted in #9, lung ultrasound exams will be done at bedside in a private location to measure the total ultrasound lung comets (an ultrasound finding for pulmonary edema) for a "comet score." One (1) single dose of 250mg acetazolamide or placebo will be given at Everest Base Camp (Data Collection #4) and a comet score will be measured again 12 hours after acetazolamide or placebo is given. Previous studies have shown that comet scores increase with altitude and given that Everest Base Camp is the highest altitude the subjects will be residing at, it is believed that we will find the biggest decrease in comet score if acetazolamide is given at this point. The subject's heart rate and oxygen saturation will also be collected via a pulse oximeter.

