#### **13. Data Analysis and Management\***

Previous studies in lung ultrasonography suggest that a minimum of 14 subjects will be needed to provide 80% power to detect a statistically significant difference in ultrasound lung comets. Between 20-30 total subjects are expected.

For data analysis, Fisher's exact test will be used to compare categorical variables. Continuous variables will be analyzed with paired Student's t-test. Linear regression models will be used to assess correlations between ultrasound lung comets and vital signs. In all cases p values < 0.05 will be considered significant. Data will be reported as mean +/- SD

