**21. SHARING OF RESEARCH RESULTS WITH SUBJECTS\***

Since ultrasound images will not be definitely reviewed until after the trek is completed, we will not be sharing the results with the subjects during the trek. However, as we consent each subject, they will be asked whether or not if they want the final results to be shared with them after the study is completed. If the subject chooses to have results to be shared with them, they will be contacted via subject's preferred contact method after all the ultrasound images reviewed and results have been gathered. Research results will not be shared with anyone else.

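### Comet scoring is not protected from knowledge of oxygen saturation and heart rate, so a reader-created correlation in the planned regression cannot be ruled out

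*Combined protocol and SAP*

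**What the plan says.** Section 11 has a lung ultrasound exam for a comet score at every data collection and adds that "The subject's heart rate and oxygen saturation will also be collected via a pulse oximeter". It sets no order between the scan and the oximeter reading. Section 23 has the principal investigator both collect the data and acquire the images.

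Section 26, on confidentiality, says that the data collected include "vital signs and will be recorded with ultrasound images and data collection sheet". It also says "A unique subject ID will be used to track data and link to ultrasound images", and "Final results of image interpretation by expert reviewer will be stored in an Excel spreadsheet in the UMass servers". Section 21 adds that "ultrasound images will not be definitely reviewed until after the trek is completed".

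Section 13 states: "Linear regression models will be used to assess correlations between ultrasound lung comets and vital signs". Significance is p < 0.05 throughout, and 20 to 30 subjects are expected.

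The one blinding provision, in section 11, is that the investigator does not know the arm. The available text does not mention masking the scanner or the image reader to vital signs.

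**The concern.** A regression of comets on saturation is informative only if the two were obtained without knowledge of each other. Scoring comets is a matter of interpretation. A reader who knows that saturation is low may expect edema and score more comets, and the reverse when it is normal. A scanner who has just seen the reading may search longer or save different frames. Either would produce a negative comet-saturation correlation with no physiology behind it.

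Section 13 names no other analysis that relates comets to a physiological sign, so a significant result is likely to be quoted in support of the ultrasound finding.

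There is also a route to the primary outcome in section 10. The last comet score at Everest Base Camp is taken 12 hours after dosing. If the drug changes saturation by then, a reader who knows saturation but not arm could still score the arms differently. Arm blinding alone does not close that route.

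**Working it through.** **What the text establishes**

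1. Storage: section 26 names two places for the collected data, the images and the data collection sheet, and lists vital signs among those data.
2. Scoring: the definitive reading is done from the images after the trek, by an expert reviewer.
3. Masking: to arm only, and of the investigator only.
4. Analysis: comets are regressed on the same vital signs.

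Items 1 to 3 leave open that the reader has the vital signs at hand. They do not show that the reader does.

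**No plan figure to reproduce.** The protocol gives no expected correlation or power for this regression. The minimum of 14 subjects in section 13 is for a difference in comets. It comes without an effect size, SD or named test, and it does not bear on this point.

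**How much influence would matter**

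Assumptions: one observation per subject; saturation X standard normal; true comet score e standard normal and independent of X; recorded score Y = e - bX; two-sided test at 0.05 (the protocol does not state sidedness). The value of b, in SD of score per SD of saturation, is assumed.

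- Variance of Y is 1 + b², so the induced correlation is -b/√(1 + b²). At b = 0.3 this is -0.3/√1.09 = -0.287.
- The critical |r| is t/√(n - 2 + t²). For n = 20, t = 2.101 gives 2.101/√(18 + 4.414) = 0.444. For n = 30, t = 2.048 gives 2.048/√(28 + 4.194) = 0.361.
- The false-positive rate is the proportion of simulated trials (40,000 per setting) with |r| above the critical value. A separate run of 100,000 per setting agreed to within about half a percentage point.

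| Assumed b | Induced correlation | False positives, n = 20 | False positives, n = 30 |
|---|---|---|---|
| 0 | 0 | 5% | 5% |
| 0.1 | -0.10 | 7% | 8% |
| 0.2 | -0.20 | 13% | 18% |
| 0.3 | -0.29 | 24% | 34% |

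The rate rises with n because a larger sample detects the same artefact more often. Section 9 plans six data collections, and section 13 does not say which enter the regression or how repeated measures are handled, so the table covers only a one-session analysis.

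**Route to the drug comparison.** Under the same model, the spurious between-arm difference is b times the drug's effect on saturation in SD units. If b were 0.3 and the shift 0.5 to 1 SD, it would be 0.3 × 0.5 = 0.15 to 0.3 × 1 = 0.30 SD. The documents give neither factor, so this shows the form of the bias and does not estimate it.

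**The case against.** The strongest reply is that the quoted sentence concerns record keeping in a confidentiality section. Its grammatical subject is the collected data as a whole. It could mean that images hold the ultrasound data and the sheet holds the vital signs, or only that both are gathered at one session. Linking by subject ID fits separate records at least as well as saturation filed with the image. Definitive reading after the trek also separates scoring from the bedside oximeter. All of this stands. A reader might infer from section 26 that saturation is in the reviewer's view and that comet scores are in fact dependent on it. The documents do not support that.

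Section 11 also refers to an attached grant proposal for the ultrasound methods, and that attachment is not available here. It might mask the reader. The reference is to the methods of scanning, however, and if the attachment does mask the reader, the wording of section 26 should be reconciled with it.

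The regression is neither the primary nor the secondary outcome in section 10, and the protocol gives it no formal validating role. That limits the weight of the point. It does not remove the route to the comet outcome itself.

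Finally, every value of b is assumed, and at b = 0 the test keeps its 5% level. That is correct: the table shows sensitivity, not an expected error rate.

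**Conclusion.** The point holds as a gap in protection. The recording rule in section 26 allows vital signs to accompany the images, nothing in the available text masks the reader or the scanner to them, and section 13 then correlates the two. A reader-created correlation cannot be ruled out. With 20 to 30 subjects, an assumed influence of 0.2 to 0.3 SD per SD would raise the false-positive rate from 5% to between 13% and 34%, given one session per subject and no true correlation.

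A reader might go further and conclude that the drug comparison is biased. That needs three things the documents do not supply: that the reader sees saturation, that the reader shades scores by it, and that a single dose shifts saturation at 12 hours. The route is possible even with intact arm blinding, but its size is unknown. The point supports a cheap improvement; it does not show that any planned result is invalid.

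**What to change.** 1. Section 26: record heart rate and oxygen saturation on the data collection sheet only, and not with the image files or in any material given to the expert reviewer.
2. Section 11: take the study oximeter reading after the session's 28 images are saved, unless there is a clinical concern. This covers influence at image acquisition, which step 1 does not reach.
3. Sections 13 and 26: merge vital signs with comet scores by the existing subject ID only after the scores are final and locked.

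The cost is a few sentences of protocol wording, a changed order within each session and a separate merge step. No extra staff or scans are needed. The change should be in place before data collection, and at the latest before scoring starts, because a reader who has seen the values cannot be masked to them afterwards.

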**10. STUDY ENDPOINTS\***

Primary outcome measures: 1.) Pulmonary edema detected in lung ultrasound exams before and after taking acetazolamide.

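### The supplied text does not say that the expert image reader is masked to session or arm, or which comet scores are analysed, so the planned paired comparison is not protected against reader expectation

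*Combined protocol and SAP*

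**What the plan says.** **Reading.** Section 26 states "Digital images of ultrasound exams will be recorded for later review as described", then "A unique subject ID will be used to track data and link to ultrasound images" and "Final results of image interpretation by expert reviewer will be stored in an Excel spreadsheet in the UMass servers". No description of the reading appears in the supplied text. Section 11 refers to pages 2-5 of an attached grant proposal for the scanning methods, and that attachment was not supplied.

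**Timing.** Section 21 opens its account of result sharing with "Since ultrasound images will not be definitely reviewed until after the trek is completed". Section 11, however, speaks of a comet score being measured at the sessions themselves, including one 12 hours after the dose. Which of the two enters the analysis is not stated.

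**Blinding.** Section 11 says "Investigator will be blinded as to which arm of the study the patient is enrolled". The faculty advisor prepares the numbered envelopes and the allocation list. The expert reviewer is not mentioned. Section 23 has the principal investigator acquire the images; no section says whether that person is also the reviewer.

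**Expectation.** Section 11 says "Previous studies have shown that comet scores increase with altitude" and, of dosing at Everest Base Camp, "it is believed that we will find the biggest decrease in comet score if acetazolamide is given at this point".

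**Outcome and test.** The primary outcome in Section 10 is "Pulmonary edema detected in lung ultrasound exams before and after taking acetazolamide". Section 13 gives a paired Student's t-test for continuous variables, Fisher's exact test for categorical ones, and a 0.05 significance threshold.

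**The concern.** A comet score is a visual count over 28 images per session. Such a count depends on judgement, and judgement can follow what the reader expects to see. The plan sets out the expectation in advance: scores rise on the way up, and fall after the dose.

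Masking to arm protects a comparison between arms. It does not protect a comparison between sessions within the same people. A reader who knows that one clip is Data Collection 4 and another is Data Collection 5 can, without intending to, score the second lower in both arms. The primary outcome is worded as a before/after contrast and the only test named for a continuous score is paired, so the analysis as written is the kind that masking to session would protect. Any description of change with altitude from Data Collection 1 to 4 is open to the same effect.

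At stake is whether a reported fall after dosing, or a rise with altitude, could partly come from the reading.

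**Working it through.** **1. What is and is not stated**

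| Question | Supplied text |
|---|---|
| Who is blinded to arm? | The investigator (Section 11) |
| Is the expert reviewer blinded to arm? | Not stated |
| Is the reviewer masked to session, altitude or pre/post-dose status? | Not stated |
| Are clips re-coded or read in random order? | Not stated |
| Which scores are analysed, bedside or post-trek? | Not stated |
| Is the expected direction known beforehand? | Yes (Section 11) |
| Which test is named for a continuous score? | Paired t-test (Section 13) |

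**2. The plan's own figure**

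Section 13 gives a minimum of 14 subjects for 80% power. It gives no effect size, SD or sidedness and does not tie the figure to a test, so it cannot be reproduced. Solving backwards for a two-sided 0.05 paired t-test with n = 14 gives a detectable change of 0.81 SD of the paired difference. This point does not challenge the 14; the 0.81 only gives a scale for the shifts below.

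**3. Illustration: within-arm paired test with no true change**

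Inputs: two-sided alpha 0.05 (sidedness is assumed); 10 or 15 per arm, from the expected 20-30 subjects split in half; a reader shift of b SDs of the paired difference. The documents give no value for b, so a range is assumed.

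The paired t statistic then follows a noncentral t distribution with n - 1 degrees of freedom and noncentrality b x sqrt(n). The rejection rate is

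P(T > t_crit) + P(T < -t_crit), where t_crit is the 97.5% point of the central t.

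- n = 10: t_crit = 2.262. For b = 0.3 the noncentrality is 0.3 x sqrt(10) = 0.949, and the rejection rate is 13.6%.
- n = 15: t_crit = 2.145. For b = 0.3 the noncentrality is 0.3 x sqrt(15) = 1.162, and the rejection rate is 19.2%.

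| Assumed shift b (SD) | 10 per arm | 15 per arm |
|---|---|---|
| 0 | 5% | 5% |
| 0.1 | 5.9% | 6.5% |
| 0.2 | 8.8% | 11.2% |
| 0.3 | 13.6% | 19.2% |
| 0.5 | 29.3% | 43.8% |

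**4. The same shift in a between-arm comparison**

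Write the change in each arm as true change plus b. If the reader does not know the arm, b is the same in both and drops out of the difference: (d_A + b) - (d_P + b) = d_A - d_P. Simulation with 100,000 runs per case, equal shifts of 0, 0.25 or 0.5 SD and 7, 10 or 15 per arm gave false-positive rates of 4.9-5.1%. The inflation in step 3 is therefore confined to within-subject comparisons.

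**The case against.** **Silence does not mean unmasked.** A reader might infer that the plan has the expert score clips in full knowledge of the session. The documents do not support that. The two sentences in Section 26 concern storage and de-identification, a subject ID identifies a person and not a session, and no section says that the reader sees date or altitude. The grant proposal might describe the reading. This stands: the defect is an omission in the supplied text.

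**Randomisation with placebo already protects the drug effect.** A reader might infer that session knowledge would create a false drug effect in the randomised comparison. If the reader is blind to arm, it largely would not, as step 4 shows. This stands too, with two limits: blinding to arm is not stated for the reviewer, and the plan names no between-arm test for a continuous score.

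**The inflated error rates belong partly to the choice of test.** A within-arm before/after test cannot separate drug from acclimatisation or time even with perfect reading. Section 10 could also be read as a yes/no outcome, for which Section 13 offers Fisher's exact test. Both are fair. They limit what the table in step 3 shows, but they do not remove the need for a masked reading, which a yes/no call needs as well.

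**The expectation is weaker than it looks.** The predicted fall is in those given the drug, so an arm-blind reader has less reason to expect one in every post-dose clip. No altitude-trend endpoint is listed. And at 0.1 SD the effect is small. All of this argues for moderate weight. It does not justify leaving the reading undescribed.

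**Conclusion.** The point holds as an omission that should be corrected. The supplied text blinds the investigator to arm. It does not state that the reviewer is masked to session, altitude, pre/post-dose status or arm, and it does not identify the analysed scores. The within-subject before/after comparison and any account of change with altitude are therefore not protected by anything written.

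The size cannot be derived from the documents. For assumed shifts of 0.1 to 0.5 SD, the within-arm false-positive rate runs from about 6% to 29% with 10 per arm and from 6.5% to 44% with 15. These figures assume a two-sided test, no true change, normally distributed paired differences and the same average shift in every subject. They are not estimates of bias in this trial, and they do not apply to a between-arm comparison of change read by someone blind to arm.

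**What to change.** Add a short paragraph on image reading to Section 11 or 13:

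1. After the trek, copy all clips to random file codes. Remove subject ID, date and time, session, altitude and vital signs, including anything printed on the image. Time matters because Data Collections 4 and 5 share one itinerary date.
2. Have the expert reader already planned score the clips in random order across subjects and sessions. State who this is, and that the reader does not hold the allocation code.
3. State that these masked readings, and not bedside counts, are the analysed comet scores.
4. Lock the score file before the session key and the allocation code are joined to it.

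If the grant proposal already provides for this, bring the wording into the plan.

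**Cost.** About 20 x 6 = 120 to 30 x 6 = 180 sessions, or 120 x 28 = 3,360 to 180 x 28 = 5,040 images, must be re-labelled by script and checked for dates or other marks left on the image. No extra reader, scan or subject is needed, and the sample size is unchanged. The definitive reading already takes place after the trek, when all clips exist and can be shuffled. One limit remains: masked reading cannot undo choices made while scanning, when the operator knows the session.

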**H00014860 Acetazolamide on High-Altitude Pulmonary Edema**

**Version 2 – 02/10/2018**

**INVESTIGATOR STUDY PLAN**

**27. PROVISIONS TO PROTECT THE PRIVACY INTERESTS OF SUBJECTS**

Ultrasound exams will take place in a private room without the presence of others. Since it might require subject to expose their thoraces briefly, a bedsheet or similar barrier available in the lodging will be used to cover the subject during their exposure. We will not access any protected health information.

